11 DISCONTINUATION AND REPLACEMENT OF PARTICIPANTS

11.1 Early Discontinuation of Study Drug

A participant may be discontinued from study treatment at any time if the participant or the investigator feels that it is not in the participant's best interest to continue. The following is a list of possible reasons for study treatment discontinuation:

- Participant withdrawal of consent
- Participant is not compliant with study procedures
- Adverse event that in the opinion of the investigator would be in the best interest of the participant to discontinue study treatment
- Protocol violation requiring discontinuation of study treatment
- Lost to follow-up
- Sponsor request for early termination of study
- Positive pregnancy test or breastfeeding (females)

If a participant is withdrawn from treatment due to an adverse event, the participant will be followed and treated by the Investigator until the abnormal parameter or symptom has resolved or stabilized.

All participants who discontinue study treatment should come in for an early discontinuation visit as soon as possible and then should be encouraged to complete all remaining scheduled visits and procedures.

All participants are free to withdraw from participation at any time, for any reason, specified or unspecified, and without prejudice.

Reasonable attempts will be made by the investigator to provide a reason for participant withdrawals. The reason for the participant's withdrawal from the study will be specified in the participant's source documents (refer to early termination procedures).

12.3 Withdrawal of Participants from the Study

A participant may be withdrawn from the study at any time if the participant, the investigator, or the Sponsor feels that it is not in the participant's best interest to continue.

12.4 Replacement of Participants

Participants who withdraw from the study treatment before last day of study drug dosing will be replaced by another enrolled participant to maintain total study numbers.

The CRF will document the reason for the withdrawal and date of withdrawal. Date of withdrawal will be documented as the date of last study drug treatment, not the date that the decision to withdraw treatment was made.

Participants will be followed after withdrawal from the study for 3 calendar days after cessation of treatment. All adverse events during that period will be reported.

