	
study single body changes occurring during pregnancy will alter the study results.
 
22. Recent vaccination within the last 2 weeks prior to study baseline visit. Routine or standard of care vaccinations (such as SARS-CoV-2, influenza, pneumococcal, and meningococcal vaccinations) are allowed but must be administered greater than 14 days prior to baseline study visit. For SARS-CoV-2 vaccination, the last dose must be administered at least 14 days prior to baseline study visit.

TEST PRODUCT, DOSE, AND ROUTE OF ADMINISTRATION	
Oral methamphetamine hydrochloride (10 mg, then 15 mg) will be administered in a double-blind fashion and prepared by over-encapsulating commercially available drug with cornstarch.

CONTROL PRODUCT, DOSE AND ROUTE OF ADMINISTRATION	
Placebo capsules will be administered in a double-blind fashion and prepared by over-encapsulating cornstarch.

DURATION OF PARTICIPANT PARTICIPATION AND DURATION OF STUDY	
Participants will be randomized to either of two treatment arms, oral methamphetamine or placebo, using a crossover design with a 31-day washout period in between treatment arms. Participants will be on study for up to 146 days.
 
Screening (for each arm): up to 14 days prior to treatment arm.
 
Treatment (for each arm): 1 day (participants to be admitted to outpatient research unit for a total of 5 hours on the treatment day)
 
Follow-up (for each arm): 31 days after the initial dose for that treatment arm.
 
The total duration of the study is expected to be 146 days (approximately 5 months).

CONCOMMITANT MEDICATIONS	
Prohibited:
 
Strict criteria for potential medications that could interact with the study drug will be used, and the following medications are not allowed during the study because of potential interactions with the study medication: acebropyline, iobenguane, isocarboxazid, methylene blue, moclobemide, phenylzine, procarbazine, rasagiline, safinamide, selegiline, tranylcypromine, asunaprevir, bupropion, topical cocaine, fluoxetine, iohexol, linezolid, paroxetine, potassium citrate, quinidine, sodium bicarbonate, sodium citrate, sodium lactate, tipranavir, and tromethamine. This is because the study medication may alter metabolism of the drugs.
 
Allowed:
 
Otherwise, participants may use their usual medications, as long as they are medically necessary and can be monitored safely during the study period.

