8 STUDY TREATMENTS

8.1 Method of Assigning Participants to Treatment Groups

Participants will be randomized to either oral methamphetamine versus placebo treatment first using a random number generator. Whichever treatment the participant receives first, they will receive the other treatment (placebo or oral methamphetamine) for their second treatment phase starting at Day 77 (See Study Events Table in Other Documents).

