10.2.1 Serious Adverse Experience Reporting

The study site will document all SAEs that occur (whether or not related to study drug) per [UCSF CHR Guidelines](#). The collection period for all SAEs will begin after informed consent is obtained and end after procedures for the final study visit have been completed.

In accordance with the standard operating procedures and policies of the local Institutional Review Board (IRB), the site investigator will report SAEs to the IRB.

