10.3 Monitoring

During the study, safety will be monitored by a Safety Monitoring Committee (SMC), which will be led by a qualified UCSF faculty member in the Department of Medicine with expertise in HIV clinical research (see Section 13 below). The SMC will review all study procedures before the initiation of the study. They will have the full and final authority to stop the study for any safety concern at any point. The Principal Investigator will be the primary medical monitor responsible for study adverse event monitoring and will report adverse events and unanticipated problems to the UCSF IRB and the SMC. All participants will be followed for possible adverse events and unanticipated problems throughout the study period.

Participants will be monitored in an outpatient clinic during the first 6 hours post-dose on dosing days. At each visit, participants will be assessed for any new symptoms, and a study coordinator will obtain vital signs. The study will require 48-hour reporting of all laboratory values, signs/symptoms, and serious adverse events (SAEs). The study will have intensive Phase I safety monitoring, which will include regular and frequent team review (every week for the first 2 months of the study; then every two weeks thereafter) of all reported events. In addition, for any Grade 3 or 4 events, sites will be instructed to contact the study team by email.

- Grade 1 or 2 Toxicity: Participants who develop a Grade 1 or 2 AE or toxicity may continue study treatment. If a participant chooses to discontinue study treatment, the site should notify the study protocol core team as noted above, and encourage the participant to complete any remaining study visits.
- Grade 3 or 4 Toxicity: Participants experiencing Grade 3 or 4 AEs requiring permanent discontinuation of study treatment should be followed closely for resolution of the AE to Grade ≤ 3 and the protocol core team must be notified. Participants discontinuing study treatment should be encouraged to complete any remaining study visits.

[name] will be contacted directly to report medical concerns or questions regarding safety.

[contact]

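### Section 12.4 dates withdrawal to the last dose and limits follow-up to 3 days after treatment ends, which does not fit one-day dosing and is not reconciled with Sections 9.1.7, 10.3 and 11.1

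*Combined protocol and SAP*

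**What the plan says.** Section 12.4 (printed under heading 11) first provides for replacing people who stop study treatment before the last dosing day. It then sets two rules.

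- Date on the CRF: "Date of withdrawal will be documented as the date of last study drug treatment, not the date that the decision to withdraw treatment" was made.
- Follow-up: "Participants will be followed after withdrawal from the study for 3 calendar days after cessation of treatment". AEs in that window are to be reported.

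The schedule is short. The synopsis gives "Treatment (for each arm): 1 day" and "Follow-up (for each arm): 31 days after the initial dose for that treatment arm". Under Section 8.1 participants cross over to the other treatment "for their second treatment phase starting at Day 77".

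Other sections are wider.

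- Section 10.3: "All participants will be followed for possible adverse events and unanticipated problems throughout the study period". It also asks that people who stop treatment be encouraged to finish their visits.
- Section 9.1.7 has AE information gathered for as long as the study runs and entered on the CRF.
- Section 11.1, for someone taken off treatment because of an AE: "the participant will be followed and treated by the Investigator until the abnormal parameter or symptom has resolved or stabilized". Everyone who stops treatment is asked to attend an early discontinuation visit and is then encouraged to attend the rest.

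No section says which of these rules takes precedence.

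**The concern.** A short window counted from the last dose can work when a drug is taken daily and people leave at about the time they stop taking it. Here drug is given on one day, and weeks of observation follow. Someone can leave long after the last dose, when the window meant to follow the withdrawal has already run out.

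Two things are at stake. The first is safety follow-up. AE incidence is the safety evaluation (synopsis and Section 5.2), and Section 2.1 relies on viral loads on days 2 and 31 of each arm when it discusses the risk of resistance. The day 31 check lies outside a 3-day window.

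The second is monitoring. Under Section 10.4 the Safety Monitoring Committee (SMC) reviews how many people have gone off study and how complete follow-up is. If the CRF holds only the back-dated date, every withdrawal after a dose appears to fall on a dosing day. With 10 participants, one misdated withdrawal is 1/10 = 10% of the sample.

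**Working it through.** The plan gives no figure to reproduce, so the check is calendar arithmetic followed by a comparison of the sections.

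**Inputs**

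- Dosing: 1 day per arm (synopsis).
- Second phase: Day 77 (Section 8.1).
- Post-dose visits: Days 2 and 31, then Days 78 and 107 (Section 9.1.4).
- Window: 3 calendar days from the end of treatment (Section 12.4).
- First dose: Day 0 or Day 1. Section 9.1.3 calls Entry Day 0. The visit numbering implies Day 1: if Day 77 is day 1 of the second arm, its days 2 and 31 fall on 76 + 2 = 78 and 76 + 31 = 107, which matches Section 9.1.4. Both are carried through.

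**Formulas**

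Window closes = dose day + 3. Gap = day of withdrawal − day the window closes.

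| Last dose | Window closes | Withdrawal on | Gap |
|---|---|---|---|
| Day 0 | 0 + 3 = Day 3 | Day 31 | 31 − 3 = 28 days |
| Day 1 | 1 + 3 = Day 4 | Day 31 | 31 − 4 = 27 days |
| Day 0 | Day 3 | Day 76 | 76 − 3 = 73 days |
| Day 1 | Day 4 | Day 76 | 76 − 4 = 72 days |
| Day 77 | 77 + 3 = Day 80 | Day 107 | 107 − 80 = 27 days |

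Day 76 is the eve of the second phase, so it is the latest possible withdrawal between phases. The last row applies only if 12.4 also covers people who leave after their second dose. Its opening sentence, on replacement, does not.

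**What closes the window early**

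The follow-up sentence counts from the end of treatment in its own words. The window would therefore close early even without back-dating. Back-dating is a separate defect: it removes the true date of leaving from the record. The rule also gives no date for someone who withdraws before any dose.

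**Who the rule covers**

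Within 12.4, the opening sentence concerns withdrawal from study treatment and the dating sentence concerns the decision to withdraw treatment. The follow-up sentence speaks of withdrawal from the study but counts from the end of treatment. Section 11.1 in turn lists withdrawn consent and loss to follow-up among its reasons for stopping treatment. The two groups overlap, and the text does not separate them.

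The overlap is practical. Section 10.4 provides for a participant to be taken off the study on the dosing day for blood pressure or heart rate. For that person 12.4 gives 3 days, while 11.1 and 10.3 give open-ended or study-long follow-up.

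**The case against.** The strongest reply is that 12.4 does not set the AE collection period. Section 9.1.7 collects AEs throughout, and Section 10.1 has the investigator ask about them at every visit and enter them on the CRF. Section 12.4 says AEs in the 3 days are reported. It does not say that others are discarded, and the 3 days could be a minimum. The follow-up sentence may also concern only people who leave the study altogether, whereas 11.1 concerns people who stop drug and stay for visits, which are only encouraged.

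Much of this stands, and it rules out several stronger readings that a reader might infer.

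- *AEs seen before a late withdrawal are lost.* Not supported: they should already be on the CRF under 9.1.7 and 10.1.
- *Anyone who withdraws has follow-up cut from 31 days to 3.* Not supported: someone who leaves after the Day 31 visit has completed that arm's follow-up, and its viral load was already due. The shortfall concerns people who leave soon after a dose.
- *Exposure time is understated.* Not supported: with one dosing day per arm the last-dose date records drug exposure correctly, and Section 14 plans no exposure-adjusted AE rate.
- *Section 10.2.1 is an equally direct conflict.* It says SAE collection is to "end after procedures for the final study visit have been completed", but it covers SAEs only, and the final visit could be the early discontinuation visit.

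The reply does not remove the problem. The text does not call the 3 days a minimum, does not confine the rule to full withdrawal, and does not require the decision date to be kept.

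**Conclusion.** The point holds as an unreconciled rule with a limited effect. Taken literally, the 12.4 window closes on Day 3 or 4 for anyone whose last dose was in the first phase. That is 27 to 28 days before a withdrawal at the Day 31 visit and up to 72 to 73 days before one on the eve of the second phase. This conflicts with 9.1.7, 10.3 and 11.1.

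Two things are exposed: events and checks after the 3 days in people who leave soon after a dose, and the off-study timing and follow-up completeness put before the SMC.

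The conclusion assumes that 12.4 is applied as written and that the first dose falls on Day 0 or 1. A site that followed 9.1.7 and 10.3 instead would collect more, so the size of any loss depends on which rule the site follows. The documents do not settle that, and this review does not say which follow-up rule is right.

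**What to change.** 1. Record two dates on the CRF: the last study drug dose and the actual date of the withdrawal decision. Give off-study timing to the SMC with both dates available.
2. State whether 12.4 applies to stopping treatment, to leaving the study, or to both, and say how someone who withdraws before any dose is dated.
3. Reconcile the 3-day window in 12.4 with 9.1.7, 10.3 and 11.1 so that one AE collection period applies to each kind of withdrawal. The length of that period is for the investigators and the SMC to decide.

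The cost is protocol wording and one CRF field. No new visit is needed.

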12 PROTOCOL VIOLATIONS

A protocol violation occurs when the participant or the study investigator fails to adhere to significant protocol requirements affecting the inclusion, exclusion, participant safety and primary endpoint criteria. Protocol violations for this study include, but are not limited to, the following:

- Failure to meet inclusion/exclusion criteria
- Use of a prohibited concomitant medication

Failure to comply with Good Clinical Practice (GCP) guidelines will also result in a protocol violation. The Principal Investigator will determine if a protocol violation will result in withdrawal of a participant.

When a protocol violation occurs, it will be discussed with the investigator and a Protocol Violation Form detailing the violation will be generated. A copy of the form will be filed in the site's regulatory binder and in the Sponsor's files.

13 DATA SAFETY MONITORING

Safety monitoring will include team review of adverse events (including all reported signs/symptoms, laboratory abnormalities, diagnoses, and SAEs) and team assessment as to the possible relationship of adverse events to the study treatment. The review will also include assessment any participants with an unconfirmed CD4+ T cell or HIV RNA measurement indicating a potential safety endpoint. Regular team monitoring will also assess early study discontinuations and visit/sample completeness. In addition, study accrual and baseline characteristics of study participants will be reviewed periodically during accrual. After a dose cohort has completed accrual and sufficient follow-up time is available, the team will evaluate whether to dose-escalate and open the next dose cohort to accrual, as described below.

Safety Monitoring Committee (SMC). We have established an independent Safety Monitoring Committee (SMC) for this study which include well-recognized experts in HIV clinical care and research: [name] (Associate Professor of Medicine, UCSF, and Director of the Division of Substance Abuse and Addiction Medicine) and [name] (Professor of Medicine, UCSF, and expert on HIV management and clinical trials). The committee will be chaired by [name] who has experience in the regulatory aspects of clinical trials and will independently deliberate using study data.

The SMC will meet after completion of each dose cohort to review safety data. The meeting will occur no earlier than two weeks after the last dose. The decision to move to the next dose cohort will be made by the SMC, after consultation with the study investigators.

A study data coordinator will produce administrative reports regularly describing study progress including the following: (1) accrual, (2) demographics, (3) study subject status,

(4) laboratory data, and (5) number and type of serious AEs. Reviews will be communicated to the UCSF Committee on Human Research (CHR), study sponsor, and/or federal agencies, as appropriate. The SMC will have access to treatment assignment. The study will be discontinued if the SMC determines that it is in the best interest of the subjects.

Grade 1 or 2 AEs will not result in any change to the study plans. If there is evidence for a Grade 3 AE that is not caused by the study drug, the study will continue as planned. On the other hand, Grade 3 AEs thought to be possibly caused by the intervention and any Grade 4 AEs will result in a hold on any future enrollments until a decision to proceed or to stop the study is made by the SMC

14 STATISTICAL METHODS AND CONSIDERATIONS

14.1 Data Sets Analyzed

[name] and her computational data specialist will be performing the data analysis for the study.

14.2 Demographic and Baseline Characteristics

The following demographic variables at screening will be summarized by dose level: race, gender, age, height and weight.

14.3 Analysis of Primary Endpoint

Paired analyses using Wilcoxon signed rank tests will be performed to evaluate whether there is a statistically significant change in markers of immune activation (e.g., CD69, CD38, and/or HLA-DR) on CD4+ and CD8+ T cells, as well as log-transformed levels of plasma cytokines (e.g., IL-6, IL-1b, IFN- γ) after study drug compared to baseline (reference will be the average of the three baseline measures). Multivariate analyses will then be performed to evaluate the association between study drug and measures of immune activation at post-dosing, using linear mixed effects models, which account for within-participant correlation of observations and allows for greater stability in the estimate of the outcome measures within individuals. Similarly, for measures of the HIV transcription, linear mixed effects regression to compare CA-US RNA levels before and after study drug will be performed. Negative binomial mixed effects regression (a method to analyze over-dispersed count data) to compare plasma HIV RNA levels before and after study drug administration (reference will be the average of three baseline measures).

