EFFICACY EVALUATIONS	
 • HIV virus replication • Immune activation (cell surface immune marker expression by flow cytometry) • Inflammation (plasma cytokine levels) • Gene expression changes (RNA-seq) • Trace amine receptor 1 (TAAR1) signaling
PRIMARY ENDPOINT	
 • HIV virus replication
SECONDARY ENDPOINTS	
 • Immunologic effect on inflammation (immune marker expression, plasma cytokine expression). • Gene expression changes • Trace amine receptor 1 (TAAR1) metabolite production
OTHER EVALUATIONS	
SAFETY EVALUATIONS	Incidence of adverse events
PLANNED INTERIM ANALYSES	
During the study, safety will be monitored by a Safety Monitoring Committee (SMC), which will be led by an HIV specialist. The SMC will review all study procedures before the initiation of the study. They will have the full and final authority to stop the study for any safety concern at any point. The decision to proceed with further drug administration will be taken by the Principal Investigator, taking into consideration clinical and laboratory adverse events. The decision to proceed with the next dosing level will be taken by the SMC. Specifically, dosing will be stopped and the SMC will be notified if one Grade 4 or two Grade 3 drug related adverse events or laboratory abnormalities are reported, becomes pregnant or initiates

	
breastfeeding, or is required to initiate one of the prohibited concomitant medications listed in section 7.1. If stopping/pausing criteria are not met, the remainder of the dosing cohort will be enrolled/dosed the subsequent week. The study will proceed to the next dosing level provided the stopping/pausing criteria are not met. A UCSF Department of Medicine faculty member who is not otherwise involved in the study and who will not communicate with the study investigators regarding any aspect of the SMC reports will prepare the monitoring reports. The SMC will review accrual, adverse events summaries, CD4+ T-cell counts and HIV RNA levels/suppression over time, off-study rates and completeness of follow-up, by dose cohort.

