
STATISTICS Primary Analysis Plan
	
[name] has expertise in epidemiology and biostatistics. Differences in residual viral transcription by MA exposure will be evaluated using multivariate negative binomial regression, as previously described. Potential covariates will include age, gender, nadir CD4+ T cell count, pre-ART HIV RNA, recent CD4+ T cell count, timing of ART (estimated date of HIV infection to date of ART initiation), duration of ART suppression, and other illicit use (stimulant or opioid exposure detected on qualitative urine measurement). Linear regressions will be used to associate MA concentrations with urinary \square-PEA levels. For the RNA sequencing data, within-individual differential gene expression analyses will be performed for each tissue type (blood and lymph node) and for each cell type (Tcm CD4+ T cells or CD14+ monocytes). Deconvolution of cell-specific gene signatures⁶⁹ will be performed to allow analysis of further cell subsets (e.g., “classical” vs. “non-classical” monocytes). For DNA variant analyses, SNP-based association tests between variants and TAAR1 signaling biomarkers will be performed using PLINK/SEQ, while gene-based association tests will be performed using SKAT-O, which aggregates variants across a region and assesses whether the number of variants with non-zero effect sizes within that region exceeds that of chance expectation. Genes and pathways will be filtered for those associated with changes in viral transcription using several pathway sources - e.g., Ingenuity Pathway Analysis (IPA), KEGG, MsigDB (Broad), and Damian Chaussabel’s immune modules. Functional Annotate Network (FAN) will be built using Genes2FANs and Cytoscape to show the key functional network elements that are downstream of candidate genes. String (string-db.org) will be used to build protein-protein interaction networks from the differentially expressed gene lists. Finally, graph theory analysis will be used to identify the functional motifs of the network.

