3 STUDY OBJECTIVES

3.1 Primary Objective

Determine whether short-term MA exposure increases residual viral production, markers of inflammation (plasma cytokine levels), and cell surface immune marker expression (flow cytometry) in blood.

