5 CRITERIA FOR EVALUATION

5.1 Primary Efficacy Endpoint

There is not a primary efficacy endpoint aim for this phase IV study, though we will be reporting changes in measures of HIV transcription, immune activation, and inflammation.

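### The synopsis makes HIV replication the only primary endpoint, Section 14.3 analyses immune markers, cytokines and viral outcomes together as primary, and no testing hierarchy or multiplicity rule is stated

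*Combined protocol and SAP*

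**What the plan says.** **What is primary**

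- Synopsis, endpoint rows: the only primary endpoint is "HIV virus replication", with no assay named. The secondary list opens with "Immunologic effect on inflammation (immune marker expression, plasma cytokine expression" and continues with gene expression and TAAR1 metabolites.
- Section 3.1, and the same objective in the synopsis: the primary objective asks whether short-term exposure "increases residual viral production, markers of inflammation (plasma cytokine levels), and cell surface immune marker expression". All three domains are joined.
- Section 5.1: "There is not a primary efficacy endpoint aim for this phase IV study, though we will be reporting changes in measures of HIV transcription", together with immune activation and inflammation.
- Section 14.3, headed Analysis of Primary Endpoint: signed-rank tests to "evaluate whether there is a statistically significant change in markers of immune activation (e.g., CD69, CD38, and/or HLA-DR", on CD4+ and CD8+ T cells, and on "log-transformed levels of plasma cytokines (e.g., IL-6, IL-1b" and IFN-gamma. It then specifies "linear mixed effects regression to compare CA-US RNA levels before and after study drug will be performed", and a negative binomial mixed model for plasma HIV RNA.

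**Error control.** Section 14.5 uses a 0.05 level for CA-US RNA without saying whether it is one- or two-sided. No testing order, alpha split, familywise rule or false discovery rate rule appears.

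**Two smaller mismatches**

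- In the synopsis row headed Primary Analysis Plan, residual viral transcription is analysed by "multivariate negative binomial regression, as previously described. Potential covariates will include age" and other factors. Section 14.4 gives the same analysis under secondary endpoints.
- Section 9.3.4 lists six analytes: TNF-alpha, IL-6, IL-10 and TGF-beta1, -2 and -3. IL-1b and IFN-gamma, named in 14.3, are not among them.

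**The concern.** A reader of the final report needs to know which result answers the primary question. On the current text that could be CA-US RNA, plasma HIV RNA, a T-cell marker or a cytokine, depending on the section used. Section 14.3 looks for statistical significance across all of them, and its lists are open-ended, so neither the number of tests nor their order is fixed. If the choice is made after the data are seen, a nominal 0.05 no longer describes the chance of a false primary claim. The sample size, by contrast, rests on one virologic outcome, CA-US RNA.

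**Working it through.** **1. The plan's own power figure.** Inputs from 14.5: n = 10, SD 0.6 log10, difference 0.5-0.6 log10, level 0.05. I assume that 0.6 is the SD of the within-person change and that the test is two-sided. For a paired t test with 9 df, the noncentrality is difference × √n / SD.

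- At 0.6: 0.6 × 3.162 / 0.6 = 3.16, power 80.3%.
- At 0.5: 0.5 × 3.162 / 0.6 = 2.64, power 65.1%.

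The stated value of about 80% is reproduced at the upper end of the range, for one test of one outcome.

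**2. How many outcomes might count.** The lists in 14.3 are examples joined by and/or, so each count below is an assumption.

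- 2: CA-US RNA and plasma HIV RNA (the synopsis governs).
- 5: one marker × 2 T-cell subsets + 1 cytokine + 2 viral.
- 9: 3 markers × 2 subsets + IL-6 (the only named cytokine on the panel) + 2 viral.
- 14: 6 marker outcomes + 6 assayed cytokines + 2 viral.

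Repeat models of the same outcome are not counted.

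**3. Chance of at least one false positive,** if each outcome is tested at 0.05 and any one success counts. For independent tests it is 1 − 0.95^m. For equal pairwise correlation r between two-sided normal tests it is 1 − ∫ φ(u) [Φ((1.96 − √r·u)/√(1−r)) − Φ((−1.96 − √r·u)/√(1−r))]^m du.

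| Outcomes m | Independent | r = 0.3 | r = 0.5 | r = 0.7 |
|---|---|---|---|---|
| 2 | 9.8% | 9.5% | 9.1% | 8.4% |
| 5 | 22.6% | 20.9% | 18.3% | 14.8% |
| 9 | 37.0% | 32.6% | 26.9% | 20.2% |
| 14 | 51.2% | 43.8% | 34.8% | 24.9% |

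The documents give no correlations; the r values are assumed.

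**4. Cytokine lists.** The named set {IL-6, IL-1b, IFN-gamma} and the six assayed analytes share only IL-6.

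**5. Threshold for secondary outcomes at n = 10.** With CA-US RNA primary, the families above leave 8 or 13 secondary outcomes, before gene expression and TAAR1 are placed. Under Holm or Benjamini-Hochberg, a single outcome that moves alone must reach 0.05/8 = 0.00625 or 0.05/13 = 0.00385. The exact two-sided signed-rank p-values are 0.0020 at W = 0, 0.0039 at W = 1, 0.0059 at W = 2 and 0.049 at W = 8. The lone outcome therefore needs W of 2 or less, or W = 0, against 8 or less unadjusted.

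**6. Separate point: power for a drug-versus-placebo contrast.** Assume 0.6 is the SD of a within-period change and r is the correlation between periods. The SD of the difference between periods is 0.6 × √(2(1−r)). With a period term, the standard error is (SD/2) × √(1/n1 + 1/n2) on 8 df. Power at 0.6 log10 with a 5:5 split is:

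| r | SD | SE | Power |
|---|---|---|---|
| 0 | 0.849 | 0.268 | 50% |
| 0.25 | 0.735 | 0.232 | 62% |
| 0.5 | 0.600 | 0.190 | 79% |
| 0.75 | 0.424 | 0.134 | 97% |

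At r = 0.5 with a 3:7 split, the SE is 0.207 and power is 72%. Sections 8.1 and 8.2 describe a random number generator and no blocking, so a 5:5 split is not assured.

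**The case against.** The plan never says that any one significant result counts as the primary result. Section 5.1 may mean only that the study claims no therapeutic efficacy, and in a ten-person mechanistic study unadjusted testing without a confirmatory claim is defensible. If the synopsis governs, just two viral outcomes are in play. This stands as a limit on the size: the error rates are conditional and the low case is 8-10%. It does not remove the contradiction. The synopsis declares a primary endpoint and also lists HIV replication under efficacy evaluations, 14.3 seeks statistical significance, and 14.5 claims power at 0.05. If the study is meant to be exploratory, the text has to say so.

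A reader might also infer that two rival models compete for the primary viral result. The documents do not support that. The synopsis row headed Primary Analysis Plan also holds the beta-PEA regression and the RNA-seq, SNP and network analyses, and it largely repeats 14.4. It reads as a general statistics row with a misleading heading. Within Section 14, a before/after mixed model for CA-US RNA and a secondary covariate-adjusted analysis can coexist.

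Nor does 14.3 commit the trial to testing IL-1b and IFN-gamma, since they are given as examples. That mismatch is a matter of aligning two lists.

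**Conclusion.** The point holds as a contradiction between current sections, not merely as missing detail. The synopsis endpoint row, the joint objective in 3.1, Section 5.1 and Section 14.3 give incompatible answers on what is primary, and nothing in the text ranks the outcomes or controls error across them.

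The size is illustrative: about 8-10%, 15-23%, 20-37% or 25-51% for two, five, nine or fourteen outcomes, over correlation 0.7 to independence. It applies only if any one significant result is taken as the primary result. A reader might infer that the plan carries a 37% or 51% false-positive rate. The documents do not support that, because they state no such decision rule and do not fix the number of tests.

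The placement of the negative binomial analysis and the cytokine lists are minor.

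**What to change.** - In the synopsis, 3.1, 5.1, 14.3 and 14.4, name log10 CA-US RNA as the single primary endpoint, tested at 0.05 with the sidedness stated, using the linear mixed model already in 14.3. It is the only virologic outcome with a power statement, and it matches the study title.
- Make plasma HIV RNA, T-cell markers and cytokines secondary, with one named adjustment (for example Benjamini-Hochberg) over a listed family, or label them exploratory. State where gene expression and TAAR1 fall.
- Label the negative binomial analysis of viral transcription secondary or sensitivity, in both the synopsis and 14.4.
- Make the cytokine list in 14.3 match the assayed panel.

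The cost is text edits, plus the stricter secondary threshold shown in step 5 if adjustment is chosen. The before/after power in 14.5 does not change.

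A related but separate point: 4.1 describes a randomised, placebo-controlled crossover, so the primary test is better based on the methamphetamine-versus-placebo difference in change from baseline, with a period term. Section 14.5 would then need restating for that contrast. Under the assumptions in step 6 its power is about 50-97%, lower if the sequences are unbalanced. That cost belongs to the change of contrast, not to naming one primary endpoint.
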